**Table 2 Power Achieved over Varying Sample Sizes and Assumed Spontaneous Abortion Rates**

Required Sample Size (mITT Analysis Population)	Assumed “True” Spontaneous Abortion Rate		
	8%	9%	10%
180	80.3%	64.8%	46.1%
240	93.1%	81.8%	63.2%
365	98.9%	94.2%	80.9%

Taking the middle of this range, a trial with 240 subjects in the mITT analysis population is considered as being adequately powered under a relevant assumption in the target population. Full simulation code is provided in [Appendix 2](#).

#### **4 Subject Disposition**

The number of subjects that discontinue the trial during the stimulation phase and after start of IMP treatment (treatment phase) will be summarized by reason for discontinuation. The subjects screened and not treated with both the IMP and the non-investigational medicinal product (NIMP), MENOPUR, will be presented in a separate data listing.

## 5 Protocol Deviations

Major protocol deviations are a subset of the important protocol deviations that may significantly impact the primary endpoint or efficacy parameters of the trial. Major protocol deviations include the following criteria:

- significant deviation in the treatment regimens of IMP and NIMP,
- use of prohibited medication, and
- non-compliance with the blastocyst transfer policy

All protocol deviations will be listed however, only major protocol deviations will be summarized in a table.

## 6 Analysis sets

### 6.1 Modified Intention-To-Treat (mITT) Cohort

The mITT cohort consists of all subjects who had successful oocyte retrieval, received at least 1 dose of IMP, and had completed fresh embryo transfer.

### 6.2 Safety Cohort

The safety cohort comprises all subjects treated with IMP.

### 6.3 Eligible Subjects (ES) Cohort

The ES cohort consists of all subjects who were deemed eligible for trial participation based on inclusion and exclusion criteria at screening and treated with oral contraceptives, leuprolide acetate, and MENOPUR

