There are 3 analysis cohorts for this trial. The mITT cohort consists of all subjects who had successful oocyte retrieval, received at least 1 dose of IMP, and had completed fresh embryo transfer. The safety cohort comprises all subjects treated with IMP. The eligible subjects (ES) cohort consists of all subjects who were deemed eligible for trial participation based on inclusion and exclusion criteria at screening and treated with oral contraceptives, leuprolide acetate, or MENOPUR.

The primary objective is to estimate the cumulative rate of any spontaneous abortion, including spontaneous clinically recognized pregnancy loss and blighted ovum during the trial (up to Week 12 following oocyte retrieval) for subjects in the mITT cohort. The number and rates of any spontaneous abortions will be summarized and associated exact 95% confidence intervals will be generated. Furthermore, as part of a Bayesian sensitivity analysis, a 95% credible interval will be generated. The spontaneous abortion rate, biochemical abortion rate, clinical pregnancy rate, and positive β -hCG rate will be similarly analyzed for the mITT and safety cohort, for subjects that had oocyte(s) retrieved. However, for these endpoints, credible intervals will not be derived. Furthermore, safety will be assessed by summarizing treatment-emergent AEs for the safety and ES cohorts. Treatment-emergent AEs will be summarized overall, by grade (intensity), seriousness, and drug relatedness by system organ class and preferred term using the Medical Dictionary for Regulatory Activities. A treatment-emergent AE is any AE that occurs after the start of PVR and through the end of the trial, or a pretreatment AE/medical condition that worsens in intensity after the start of PVR. Furthermore, a separate treatment-emergent AE summary table will be generated for AEs of special interest, such as vaginal pain and irritation, vaginal infection, vaginal bleeding/spotting, vaginal hemorrhage, vaginal adhesions and vaginal or cervical abrasions and lesions. These events will also be further analyzed by grade (intensity). Tolerability for the safety cohort will be assessed by summarizing the total number of subjects who prematurely discontinued PVR and the associated reasons for discontinuation. This summary will be based on the safety cohort.

For the safety and ES cohorts, the number of subjects with abnormal clinical laboratory and vital sign assessments will be summarized.

TABLE OF CONTENTS

SYNOPSIS.....	2

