9.3 Subject Disposition

The number and percentage of subjects treated with oral contraceptives, leuprolide acetate, MENOPUR, hCG, and IMP, and subjects who underwent a fresh cycle, will be summarized. Furthermore, the number of subjects that discontinue the trial during the suppression phase, stimulation phase, and after start of IMP treatment (treatment phase) will be summarized by reason for discontinuation. The subjects screened and not treated with either IMP nor NIMP (oral contraceptives, leuprolide acetate, MENOPUR, and hCG) will be presented in a separate data listing.

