## 10 Safety

### 10.1 General Considerations

Safety parameters will be evaluated for the ES and safety cohorts. Safety summaries will be presented by the 5 phases of the trial. These phases are defined as follows:

- Screening Phase: From the date of signing the informed consent through the day before the start of the oral contraceptive treatment.
- Suppression Phase: From the start of oral contraceptive treatment until the day before the start of the stimulation phase (start of MENOPUR treatment).
- Stimulation Phase: From the date of the first dose of MENOPUR through the day before the start of IMP.
- Treatment Phase: From the date of the first dose of IMP (PVR) through the end of the trial.
- Study Phase: From the date of the first dose of oral contraceptive through the end of the trial.

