#### 10.2.2 Incidence of Adverse Events

Treatment-emergent adverse events will be summarised in a Table by SOC and PT of MedDRA using the latest available version. The Table will display the total number of subjects reporting an AE, the percentage of subjects (%) with an AE, and the number of events (E) reported. AEs will be

---

presented by system organ class (SOC) sorted alphabetically and preferred term (PT) sorted in decreasing frequency of occurrence.

Summary tables will be prepared for:

- All Treatment-emergent adverse events
- Treatment-emergent adverse events with an incidence [ $\geq 5\%$ ] of subjects in any treatment group
- Treatment-emergent adverse events by causality (related/unrelated)
- Treatment-emergent adverse events leading to death
- Treatment-emergent adverse events by intensity
- Treatment-emergent Serious adverse events
- Treatment-emergent Adverse events leading to withdrawal
- Non-serious treatment-emergent AEs with an incidence of at least 5%

Furthermore, the overall AE summary table by system organ class and preferred term will also be produced for the study phase, suppression phase, and the stimulation phase for the ES and safety cohorts.

Supporting data listings will be provided for:

1. All treatment-emergent adverse events sorted by centre and subject number
2. All treatment-emergent adverse events sorted by MedDRA System Organ Class and Preferred Term
3. Serious adverse events
4. Adverse events leading to death
5. Adverse events leading to withdrawal.

For listings specified in 3-5, there will be a variable that will indicate which phase of the trial each event occurred.

A separate AE listing will be provided for the screening phase, suppression phase, stimulation phase, and treatment phase of the trial.

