## 12 Deviations from Protocol

The following changes and additions from the planned displays and analyses described in the previous version of the clinical trial protocol have been implemented in the statistical analysis plan:

- All 90% confidence intervals have been replaced with 95% confidence intervals based on FDA input on the statistical analysis plan.
- The embryo quality analysis that is described in this SAP was not mentioned in the clinical trial protocol.
- The definition of the Eligible Subjects cohort is taken to be a subject that has received at least one dose of oral contraceptives, leuprolide acetate, and MENOPUR. This aligns with the analogous cohort from the DR-PGN-302 study. In the clinical trial protocol, an “or” is used instead of an “and”.

These revisions have been implemented in the clinical trial protocol version 6.0.

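### The suppression-phase and study-phase AE tables cannot count any woman who stopped before MENOPUR, and the SAP drops the suppression-phase discontinuation summary that the protocol requires

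*SAP*

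**What the plan says.** **Cohorts.** SAP 6.3 and Protocol 9.5.3 define the ES cohort as women eligible at screening and "treated with oral contraceptives, leuprolide acetate, and MENOPUR". SAP 1.1.1 repeats this. SAP 12 spells it out as at least one dose of each and gives the reason: to match the corresponding cohort of DR-PGN-302. The safety cohort (SAP 6.2, Protocol 9.5.2) is everyone who received the IMP, which starts the day after oocyte retrieval.

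**Phases.** SAP 10.1 defines the suppression phase as "From the start of oral contraceptive treatment until the day before the start of the stimulation phase (start of MENOPUR treatment"). The study phase also begins at the first oral contraceptive dose and runs to the end of the trial.

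**AE tables.** SAP 10.2.2 says of the overall AE table, arranged by MedDRA class and term, that it "will also be produced for the study phase, suppression phase, and the stimulation phase for the ES and safety cohorts". Protocol 9.9.2 says the same.

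**Disposition.** Protocol 9.3 asks for a summary, by reason, of "the number of subjects that discontinue the trial during the suppression phase, stimulation phase, and after start of IMP treatment". SAP 4 covers "The number of subjects that discontinue the trial during the stimulation phase and after start of IMP treatment" and does not mention suppression.

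**Synopsis.** The protocol synopsis still defines the ES cohort as women "treated with oral contraceptives, leuprolide acetate, or MENOPUR". SAP 12, after describing the change from *or* to *and*, states: "These revisions have been implemented in the clinical trial protocol version 6.0".

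**The concern.** A table of AEs during suppression should describe the women exposed to the suppression drugs. Here a woman must first get through suppression and start MENOPUR before she can be counted. Those who stop early, including any who stop because of an AE on the oral contraceptive or leuprolide, are left out. The tabulated counts and percentages are therefore conditional on completing the phase they describe. The study-phase table has the same gap, because its window opens at the first oral contraceptive dose.

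The disposition section would be the natural place to see how many women were lost this way and why, and that is where the SAP is narrower than the protocol. A reader of the summary tables alone would see neither the events nor the attrition. SAP 2 says the trial will be judged on all the safety information collected, so a gap in a planned safety table deserves repair even though it falls before IMP exposure.

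**Working it through.** The plan states no figure for this point, so the check is mainly one of set membership.

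**Step 1. Who can enter the tables?** Take an eligible woman who starts the oral contraceptive and stops during suppression.

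| Condition | Source | Met? |
|---|---|---|
| At least one MENOPUR dose (needed for ES) | SAP 6.3 and 12; Protocol 9.5.3 | No: suppression ends the day before the first MENOPUR dose (SAP 10.1) |
| At least one IMP dose (needed for safety cohort) | SAP 6.2; Protocol 9.5.2 | No: IMP starts the day after oocyte retrieval |
| In the suppression- or study-phase AE table | SAP 10.2.2; Protocol 9.9.2: ES and safety cohorts only | No |

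No woman can both stop in suppression and belong to either cohort, so all such women are excluded.

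**Step 2. Does another AE summary table count her?** No. The tables of AEs leading to withdrawal (SAP 10.2.1 and 10.2.2) are restricted to treatment-emergent events, that is, events from the first ring onward.

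**Step 3. Where does she still appear?**
- Her AEs are collected, because recording starts at consent (Protocol 7.2.9).
- SAP 10.2.2 provides a separate suppression-phase AE listing with no stated cohort restriction.
- SAP 10.2.2 also lists SAEs, AEs leading to death and AEs leading to withdrawal, each with a phase indicator.
- SAP 4 lists screened subjects not treated with both IMP and MENOPUR. She received neither, so she belongs there whether that is read as lacking both or lacking either.

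**Step 4. Disposition side by side.**

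| Discontinuations by reason | Protocol 9.3 | SAP 4 |
|---|---|---|
| Suppression phase | Yes | Absent |
| Stimulation phase | Yes | Yes |
| After start of IMP | Yes | Yes |

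SAP 12 lists the SAP's departures from the protocol, and this one is not among them.

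**Step 5. What could it do to the percentages?** The documents give neither the share stopping in suppression nor AE rates in that phase. Everything in this step is assumed, to show how the gap behaves. Let *d* be the share of starters who stop in suppression, *c* the proportion of continuers with a suppression-phase AE, and *s* the same proportion among stoppers.

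- Rate shown in the ES table = *c*, treating ES as the continuers
- Rate in all who started = (1 − *d*)·*c* + *d*·*s*
- Difference = *d*·(*s* − *c*)
- Share of affected women missing from the table = *d*·*s* / [(1 − *d*)·*c* + *d*·*s*]

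With *c* = 10% and *s* = 50%:

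| *d* | ES table | All who started | Affected women missing |
|---|---|---|---|
| 2% | 10.0% | 0.98×0.10 + 0.02×0.50 = 10.8% | 0.010/0.108 = 9% |
| 5% | 10.0% | 0.95×0.10 + 0.05×0.50 = 12.0% | 0.025/0.120 = 21% |
| 10% | 10.0% | 0.90×0.10 + 0.10×0.50 = 14.0% | 0.050/0.140 = 36% |
| 15% | 10.0% | 0.85×0.10 + 0.15×0.50 = 16.0% | 0.075/0.160 = 47% |

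With *s* = *c* = 10% the percentage stays at 10.0%, but 2% to 15% of affected women are still missing. If *s* were below *c*, the ES table would overstate the rate. So the omission from the counts is certain, while the direction and size of the effect on the percentage are not.

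**The case against.** The other side has real substance.

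- **The table is outside the trial's main purpose.** The safety endpoints concern women treated with the ring. Suppression-phase events precede the ring and occur on commercially available products, and no endpoint is a suppression-phase AE rate. This stands and limits the weight of the point. But both documents plan a suppression-phase table, so its denominator should fit the phase.
- **The definition was deliberate and disclosed.** SAP 12 states the *and* wording and the reason for it. This stands as an explanation of the cohort. It does not show that the cohort suits events that happen before one of its entry conditions can be met. Nor do the documents plan any ES-cohort comparison with DR-PGN-302; that study's data are used only in the Bayesian sensitivity analysis of the mITT primary endpoint.
- **The women are not lost.** A reader might infer that they vanish from the report. The documents do not support that: the listings described above hold them, and SAP 10.2 requires narratives for all serious AEs. What is missing is a count, a denominator and a tabulated reason for stopping.
- **The protocol still governs.** Protocol 9.3 requires the suppression-phase disposition summary, and the SAP is written to that protocol, so the summary may be produced anyway. But Protocol 9 leaves the analysis detail to the SAP, and programming from SAP 4 alone would omit it.
- **The definition is not in doubt.** The synopsis might suggest that the ES definition is unsettled. It is not: Protocol 9.5.3 and SAP 1.1.1, 6.3 and 12 all say *and*. The revision reached the defining section, and one stale word remains in the synopsis.

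**Conclusion.** The point holds as a gap in the summary tables. Followed as written, the plan leaves every eligible woman who stopped during suppression out of the suppression- and study-phase AE tables, in numerator and denominator alike. This follows from the definitions and needs no assumption. SAP 4 separately omits a disposition summary that Protocol 9.3 requires, without declaring the departure.

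The size is unknown. The documents give no suppression drop-out rate, and the illustrative percentages rest wholly on assumed AE rates. It would be tempting to conclude that suppression-phase AE rates will be understated by a material amount. That requires stoppers to have more AEs than continuers, and enough of them, which is plausible where AEs cause stopping but is not shown in the documents.

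Nor does the point reach the trial's main conclusions. The primary mITT analysis, the sample size, and the treatment-emergent AE and tolerability analyses all concern women who received the ring and are unchanged. This is a correction worth making before database lock, not a threat to the trial's validity.

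**What to change.** 1. **AE tables (SAP 10.2.2, Protocol 9.9.2).** Produce the suppression- and study-phase AE tables on all eligible women with at least one dose of oral contraceptive or leuprolide. Keep the *and* ES cohort for its other declared uses.
2. **Disposition (SAP 4).** Restore suppression-phase discontinuations by reason, to match Protocol 9.3. If the omission was intended, declare and justify it in SAP 12.
3. **Editorial (protocol synopsis).** Change the ES definition from *or* to *and*, to agree with Protocol 9.5.3.

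The cost is one additional population flag, one disposition row and short wording changes. No new data are needed, because AEs are recorded from consent and reasons for discontinuation are already captured in the eCRF.

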## 7 Trial population

### 7.1 Demographics and Other Baseline Characteristics

Descriptive statistics for demographics and other baseline characteristics will be presented for the subjects in the mITT, safety, and ES cohorts.

Categorical data will be summarised using numbers and percentages. The percentages are based on the total number of subjects with a corresponding assessment. Continuous data will be presented, for example, using the number of subjects (N), mean and standard deviation, median, minimum and maximum. All baseline characteristics will be listed. Associated demographic listings will also be produced.

#### 7.1.1 Demographics

Descriptive statistics of screening demographics variables (e.g., age, race and ethnic origin, height, weight and BMI) will be summarized.

#### 7.1.2 Endocrine Profile

The screening AMH, FSH and E2 assessments will be summarized for the mITT and ES cohorts. Furthermore, the AMH level will be summarized by categories  $< 5 \text{ ng/mL}$  and  $\geq 5 \text{ ng/mL}$ . Values below the lower limit of quantification (LLOQ) will be included as LLOQ/2.

For stimulation day 1, E2 will be assessed by the sites. This assessment will be summarized. Values below the lower limit of quantification (LLOQ) will be included as LLOQ/2.

#### 7.1.3 Gynaecological History and Infertility Diagnosis

Gynaecological history, infertility diagnosis and menstrual history collected at screening will be summarized for the mITT and ES cohorts.

#### 7.1.4 Smoking and Alcohol Habits

Smoking and Alcohol consumption history and current habits at screening will be summarised for the mITT and ES cohorts.

#### 7.1.5 Transvaginal Ultrasound

##### Visibility of the Ovaries

The visualization of the left and right ovaries (No/Yes) will be summarized.

##### Antral Follicles

For summary of antral follicles please see stimulation day 1 analysis in [Section 9.5.1](#)

## 7.2 Medical History

Medical history recorded at screening visit will be coded using MedDRA version 21 or later.

### **7.3 Prior and Concomitant Medication**

Prior and concomitant medication will be summarised by ATC classification 1st level (alphabetically), ATC classification 2nd level (in decreasing order of frequency) and treatment group. These medications will be tabulated separately for:

- 1) Prior medication; i.e. medication taken exclusively prior to treatment with IMP (i.e. with stop date before date of first IMP administration);
- 2) Concomitant medication, i.e. medication taken during the treatment period (phase) i.e. medication that was not stopped before date of first IMP-administration and not started after the end of trial.

If the timing of the dose of a concomitant medication cannot be established in relation to the administration of IMP, it will be considered as concomitant medication. Prior-medication will be summarized for the mITT and ES cohorts while concomitant medication will be summarized for the mITT cohort.

### **7.4 Physical Examination**

Subjects with abnormalities at any screening, baseline, or post-baseline visit will be listed with all physical examination evaluations.

## **8 Exposure and Treatment Compliance**

### **8.1 Extent of Exposure**

All NIMP summary will be based on the safety and ES cohorts. In contrast, the IMP analysis will be based on the safety and mITT cohorts.

#### **8.1.1 PVR**

The total number of PVRs used and the duration of treatment will be summarized. Furthermore, the drug compliance rate will also be summarized. Compliance is defined as follows:

(number of PVRs used) / (number of PVRs expected to be used).

The number of PVRs expected to be used is defined to be the number of weeks from oocyte retrieval to either confirmation of no pregnancy via  $\beta$ -hCG test or TVUS assessment or in the case of a subject where there is no such confirmation, the end of trial visit.

The number of times a subject was unable to keep a PVR in for at least 23 hours and the number of times a subject recorded a damaged PVR will be summarized. A detailed associated listing will be produced.

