3.5.5 Selection and Timing of Dose for Each Subject

A new PVR will be inserted every 7 days, with up to 10 PVRs used through Week 12 of pregnancy (10 weeks post-oocyte retrieval).

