6.3 Treatment with PVR

6.3.1 Visit 4: Initiation of Treatment with PVR

Treatment with PVR will be initiated one day after oocyte retrieval (Visit 4).

The following must take place at the visit:

- Vital signs
- Blood collection for assessment of:
 - Clinical chemistry and hematology parameters (*Note:* if Visit 4 occurs on a day where shipment to the central laboratory is not feasible, e.g. during the weekend, the subject will return to the site for blood collection on the next possible day)
 - Endocrine parameters (progesterone and estradiol)
- Assessment of vaginal hemorrhage
- Pelvic examination (documentation of presence and grade [intensity] of any pain, irritation, abrasions, or lesions on the cervix or vagina or vaginal adhesions, see [Appendix 2](#)).
- Dispensing of IMP: the first 4 PVRs will be distributed (PVR1, PVR2, PVR3 and PVR4). Subjects will be instructed in the proper method for PVR insertion and removal (see [Appendix 1](#)). The subject will insert PVR1 while at the trial site. Subjects will be allowed to remove the

PVR for up to 1 hour/day; this includes removal for sexual intercourse, although this is not necessary.

- Provide subjects with PVR diary and instructions on how to complete the diary. Subjects will be asked to fill out the diary at home for each PVR used and bring it to each subsequent visit.
- Provide subjects with bleeding log and instructions as to how to differentiate between vaginal discharge and bleeding (to capture the frequency and intensity of any bleeding). Subjects will be asked to fill in the bleeding log at home and bring it to each subsequent visit.
- Provide subjects with sanitary napkins. Subjects will be instructed to use only sanitary napkins provided by the trial site for any bleeding that occurs during the trial.
- Recording of use of any concomitant medication
- Recording of AEs

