6.3.5 Visit 7: Week 5 of Pregnancy (3 Weeks After Oocyte Retrieval)

Subjects will attend Visit 7, 3 weeks (21±2 days) after oocyte retrieval.

The following must take place at the visit:

- Vital signs
- Blood collection for assessment of:
 - Endocrine parameters (β -hCG)
If the subject has a negative β -hCG (<5 mIU/mL), treatment will be stopped and the subject will be withdrawn from the trial and the early withdrawal visit is to occur (section 6.3.8).
- Removal of PVR3 and insertion of PVR4 (for subjects with a positive β -hCG (\geq 5 mIU/mL))
Insertion of PVR4 can be performed either at the trial site or at home.
- Review of PVR diary
- Assessment of drug accountability
- Recording of any vaginal bleeding noted in the subject's bleeding log since the previous visit
- Assessment of vaginal hemorrhage
- Recording of use of any concomitant medication
- Recording of AEs
- Dispensing of IMP: the next 3 PVRs and a replacement PVR to be used in the event of ring loss or damage (PVR5, PVR6, PVR7 and PVR-R) will be distributed.
The subjects will remove and insert the PVRs at home. Subjects will be instructed to replace the PVR every 7 days. If the replacement PVR is used, the subject should obtain another replacement PVR from the trial site as soon as possible.

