6.4 End-of-trial

The End-of-trial visit (Visit 10) occurs 12 weeks (84 ± 2 days) after oocyte retrieval (week 14 of pregnancy) / 2 weeks (14 ± 2 days) after the last exposure to IMP.

The following end-of-trial procedures / assessments must take place:

- Vital signs

- Blood collection for assessment of:
 - Clinical chemistry and hematology parameters
- Urinalysis
- Complete physical examination (including weight, and BMI calculation)
- Pelvic examination (documentation of presence and grade [intensity] of any pain, irritation, abrasions, or lesions on the cervix or vagina or vaginal adhesions).
If any lesions or abrasions are found on the cervix or vagina or vaginal adhesions are noted, another examination will be performed 2-4 days later.
- TVUS or abdominal ultrasound (pregnant subjects only) to determine the number of gestational sacs with/without fetal heart beat and estimate gestational age
- Recording of any vaginal bleeding noted in the subject's bleeding log since the previous visit
- Assessment of vaginal hemorrhage
- Recording of use of any concomitant medication
- Recording of AEs

After completion of the End-of-trial visit, subjects will be referred to their obstetricians for further care.

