9.8 Extent of Exposure and Treatment Compliance

9.8.1 PVR

The total number of PVRs used and the duration of treatment will be summarized. The total number of subjects who prematurely discontinued PVR and the associated reasons for discontinuation will also be summarized. Furthermore, the drug compliance rate will also be summarized for the mITT and safety cohorts. Compliance is defined as follows:

(number of PVRs used)/ (number of PVRs expected to be used).

These summaries will be generated for the safety cohort. Additional information collected in the drug accountability eCRF module may be summarized. A detailed associated listing will be produced.

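### The ring compliance ratio rises when a ring is replaced, so a replacement can cancel a missed week, because all rings used are set against a calendar-week expectation

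*SAP*

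**What the plan says.** SAP 8.1.1 gives the ratio as "number of PVRs used) / (number of PVRs expected to be used", and Protocol 9.8.1 gives the same ratio. Neither section says whether a replacement ring counts as used, and neither caps the result.

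Only the SAP defines the denominator. It is "defined to be the number of weeks from oocyte retrieval to either confirmation of no pregnancy" by β-hCG test or ultrasound or, "in the case of a subject where there is no such confirmation, the end of trial visit". Protocol 6.4 fixes that visit: "The End-of-trial visit (Visit 10) occurs 12 weeks" after retrieval. No rounding rule for weeks is stated.

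Replacement rings are part of the design. At Visit 7 (Protocol 6.3.5) the woman receives "the next 3 PVRs and a replacement PVR to be used in the event of ring loss or damage". Once she has used it she is to get another from the site, and no limit is given. Protocol Appendix 1 also has a fecally contaminated ring replaced. Under Protocol 7.3.6 a diary is kept for each ring used.

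SAP 8.1.1 separately summarizes total rings used, duration of treatment, failures of the 23-hour rule and damaged rings, and plans a listing.

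**The concern.** The numerator counts rings and the denominator counts weeks. The two correspond only while one ring serves one week. A replacement adds one to the numerator and nothing to the denominator, so the ratio moves up when a ring is lost or damaged.

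Two things follow. A missed week and a replacement cancel, so women with different coverage get the same score. And a woman who needed replacements scores higher than one who wore every ring without trouble. Tolerability is a stated objective of this trial. A compliance figure that improves with ring loss is a poor companion to it.

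**Working it through.** **Inputs**
- First ring: the day after oocyte retrieval (Protocol 6.3.1).
- Interval: "A new PVR will be inserted every 7 days" (Protocol 3.5.5), with at most 10 scheduled rings through week 10 after retrieval.
- End-of-trial visit: week 12 (Protocol 6.4).
- Expected rings: weeks from retrieval to confirmed non-pregnancy, otherwise to the end-of-trial visit (SAP 8.1.1).
- Replacement ring: dispensed from Visit 7, renewable (Protocol 6.3.5).
- Frequency of replacement: not given in the documents. The counts below are illustrations.

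**The plan's own figure.** With retrieval as day 0, insertions fall on days 1, 8, 15, 22, 29, 36, 43, 50, 57 and 64. That is 10 rings before day 70, which agrees with the stated maximum of 10.

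**Formula as written.** Compliance = (scheduled rings − missed + replacements) / weeks expected.

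**Woman still pregnant at the end-of-trial visit (expected = 12)**

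| Use | Ratio |
|---|---|
| All 10 rings, no replacement | 10/12 = 83.3% |
| 2 weeks missed, 2 replacements | (10 − 2 + 2)/12 = 83.3% |
| All weeks covered, 1 replacement | 11/12 = 91.7% |
| All weeks covered, 2 replacements | 12/12 = 100% |
| All weeks covered, 3 replacements | 13/12 = 108.3% |

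She passes 100% only at the third replacement.

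**Loss confirmed earlier**

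| Confirmed at | Use | Ratio |
|---|---|---|
| Week 6 (6 scheduled rings, expected = 6) | 1 replacement | 7/6 = 116.7% |
| Week 6 | 1 week missed, 1 replacement | 6/6 = 100% |
| Week 10 (10 scheduled rings, expected = 10) | 1 replacement | 11/10 = 110% |

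**Does correcting the numerator alone bound the ratio?** No. If loss is confirmed at Visit 7P, day 31 or 32, five rings have been inserted on schedule (days 1, 8, 15, 22, 29). The expected number is 31/7 = 4.43 or 32/7 = 4.57. With no replacement at all, the ratio is 5/4.43 = 112.9% or 5/4.57 = 109.4%. Rounding weeks down gives 5/4 = 125%, and rounding up gives 5/5 = 100%.

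**After correcting both parts** (scheduled periods covered / scheduled periods)
- Pregnant to the end, no week missed: 10/10 = 100%, whatever the number of replacements.
- Pregnant to the end, 2 weeks missed, 2 replacements: 8/10 = 80%.
- Loss at week 6, 1 replacement: 6/6 = 100%. With 1 week also missed: 5/6 = 83.3%.
- Loss at day 31 or 32, no week missed: 5/5 = 100%.

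**The case against.** The documents never say that replacements count. That reading comes from the unqualified wording and from the diary being kept per ring used. A programmer could exclude them. This stands, but it is a reason to write the rule down.

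A replacement may also give real extra coverage. The protocol does not say whether it completes the old seven-day period or starts a new one. If a ring is lost late in its week and its replacement is worn for seven days, the replacement supplies most of another week. This stands too. It limits how much of the rise can be called spurious, but a calendar-week denominator still cannot tell the two cases apart.

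Much is reported beside the ratio: damage counts, wear below 23 hours, duration and a listing. Missed weeks can be recovered from the diary dates. But none of this adjusts the ratio, and no count of lost or replaced rings is planned. Protocol 9.8.1 only allows further accountability data to be summarized.

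A reader might infer three stronger things that the documents do not support.
- That one or two replacements push any woman above 100%, for example 12/10 = 120%. That uses ten weeks. The SAP's denominator for a woman pregnant to the end is twelve, so two replacements give 100%. Values above 100% with one replacement arise where the denominator stops at confirmed non-pregnancy.
- That the ratio hides ring expulsion in general. Appendix 1 has an expelled ring rinsed and reinserted unless it is fecally contaminated. A reinserted ring never enters the numerator, and changing the numerator would not reveal it.
- That redefining the numerator is enough. The day 31–32 case shows that it is not.

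**Conclusion.** The point holds for the ratio as written: replacements raise it and can mask missed weeks. For a woman pregnant to the end, each replacement adds 1/12 = 8.3 percentage points. For a loss confirmed at week 6 it adds 1/6 = 16.7 points.

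This rests on counting every ring worn as used, on one ring per scheduled week, and on replacements from Visit 7 onward. Before Visit 7 an extra ring could come only from the first four dispensed or from an added dispensing, so early examples are less certain. The effect on the trial-wide mean cannot be sized without a replacement frequency.

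The denominator is the larger fault, since uninterrupted use to the end of the ring schedule scores only 83.3%. The two parts should be corrected together.

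The consequence is small. No analysis set depends on compliance, and the primary endpoint, its confidence interval and the sample size are unaffected.

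**What to change.** In SAP 8.1.1 and Protocol 9.8.1:

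1. Define the numerator as the number of scheduled weekly ring periods (PVR1 to PVR10) in which a ring was inserted. State that the periods run from insertion of PVR1 and that a second ring in the same period is not counted again.
2. Define the denominator as the number of scheduled ring periods begun up to confirmed non-pregnancy or, failing that, to the end of the planned ring schedule, at most 10. This replaces calendar weeks to the end-of-trial visit and removes the rounding question. With both changes the ratio cannot exceed 100%.
3. Report replacement rings separately, as number of women and number of rings, with the reason where the diary or the IRT records it.

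The cost is a few sentences in each document and minor programming. Insertion and removal dates and damage are diary items (Protocol 7.3.6). Dispensing, returns and the reason for missing rings go into the IRT (Protocol 5.6.1 and 5.6.2). Contamination is not a listed diary item, so reporting it as a reason may need free text or an added field. Nothing in treatment or visits changes.
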